PROTOCOL TITLE: Efficacy of a Coupler-Based Fitting Approach for Experienced Users Receiving Replacement Hearing Aids

PRINCIPAL INVESTIGATOR: [name], Au.D., Ph.D.

VERSION NUMBER AND DATE: Version 10, June 10, 2022

SPONSOR/FUNDING SOURCE: VA RR&D Merit Review C2777-R

Purpose

The overarching purpose of this project is to develop an accurate coupler-based fitting model for experienced hearing-aid users obtaining replacement hearing aids of any style that will result in positive patient outcomes while mitigating a face-to-face fitting visit.

The proposed project addresses three aims:

Specific Aim 1. Develop vent correction factors for testbox fittings of in-the-ear (ITE) and traditional behind the ear (BTE) with custom earmold hearing aids, which will be used to evaluate the real ear to complete difference (RECD)-fitting approach in a sample of experienced users receiving replacement hearing aids. Hypothesis 1a. RECD coupler-based fittings will accurately meet prescriptive targets and expected aided audibility for ITE and traditional BTE styles. Hypothesis 1b. Subjective outcomes from RECD coupler-based fittings will meet or exceed published norms.

Specific Aim 2. Develop correction factors for RECD coupler-based fittings of hearing aids with non-custom coupling (i.e., mini-BTEs with slim tubing and noncustom open canal coupling—open fits). Hypothesis 2. Correction factors will be developed to account for RECD coupler-based fittings with open canals.

Specific Aim 3. To determine if the open-fit RECD-fitting approach is equivalent to the standard of care (SoC) open-fit fitting approach. Hypothesis 3a. Derived REARs from open-fit RECD-fittings will accurately meet prescriptive targets and expected aided audibility and will be equivalent to in situ REARs in SoC fittings of open-fit styles. Hypothesis 3b. The subjective outcomes will not significantly differ between the experimental RECD-fitting group and the SoC group for open-fit styles.

Background and Significance

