Session 1 (Baseline, Pre-Fitting). All testing will be completed separately in each ear for both groups. Otoscopy will be performed. The standard audiometric evaluation including air- and bone-conduction pure-tone audiometry; word-recognition in quiet (NU-6 words) and in noise (Words-in-Noise test; Wilson et al., 2003; Wilson, 2003; Wilson and Burks, 2005) will be completed. Tympanometry and aural acoustic reflexes also will be measured. These results will be compared to the audiogram for the original fitting to rule out a significant change in hearing. The current hearing aids will be maintained and the fit will be verified via real-ear measurements. The Client Oriented Scale of Improvement (COSI) will be completed to obtain the listening goals of the participant and to facilitate programming needs of the replacement hearing aids (e.g., whether or not manual programs are needed/desired) along with outcome measures for their current hearing aids (presented in random order). Obtaining subjective outcomes from their current hearing aids will provide baseline scores for which to compare outcomes from the replacement hearing aids to ensure the outcomes from the replacement hearing aids are at least equivalent. In addition, an intake form (See Appendix) will be completed for both groups to determine other device options and function (e.g., volume control options such as yes/no or unlinked/linked; removal filament or not; earmold style from previous order form; etc. The participant will be asked to demonstrate hearing aid skills with their current hearing aids. If questions or concerns arise, then they will be re-oriented during this session or disqualified. Earmold impressions will be taken for replacement hearing aids. For the BTE group, only acrylic earmold material will be used.

For both groups, RECD values will be obtained separately for each ear with the foam insert following the ANSI S3.46 (2013) standard as implemented in Audioscan Verifit 2 system. In

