Study 1 Power Analysis. The primary outcome of interest is based on fitting accuracy of each ear (i.e., deviation of REAR from prescriptive target across frequency). A power analysis for a repeated measure ANOVA with an effect size $\eta^2 = 0.10$, power ($1-\beta$) = 0.80, and $\alpha = 0.05$ requires a sample size of 100 ears (total of 50 participants) over the two groups. A small effect size is expected, as a small effect size was found in the preliminary data ($\eta^2 = 0.10$). Considering 15% attrition, then 8 additional participants will be needed ($N = 58$) resulting in 29 participants per group.

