Study 1 Data Analysis Plan. A generalized linear model will be applied to examine fitting accuracy. This analysis will examine differences (in dB SPL) for in situ REAR (based on testbox fittings) across frequency between the groups relative to the prescription. Because it is expected that differences within the two ears of the same subject will be smaller than differences across subjects, inclusion of both ears in the same analysis may over inflate the statistical power. However, it is also of interest to ensure that all data are considered. Therefore, we propose to complete separate analyses for the left and right ear, even though we expect the pattern of results to be very similar for each ear. These analyses will determine (1) in situ REARs of the testbox fittings matched the prescription within each group, and (2) if there was an effect of fitting accuracy as a function of style. A generalized linear model will be conducted to compare the expected (from prescription) and actual aided SII within and between groups. Finally, separate mixed model repeated measures ANOVA will be applied to examine group differences among the outcome measure subscales (i.e., SADL subscales, IOI-HA items/subscales, and for the APHAB subscales) to examine differences in outcomes between groups and between current hearing aid fittings and the replacement testbox fittings. For the COSI, the percentage of 'better' and 'much better' responses and the average of the final ability will be calculated across goals and compared between groups via a paired-sample t-test. The subjective outcomes of replacement hearing aids (Session 3) from testbox fittings will also be compared to normative data for each group by comparing our mean, standard deviation, and sample size to those same variables from the published outcome respectively via a Welch test. This will inform whether our outcomes for testbox fittings of replacement hearing aids from each group were consistent with the published norms or not. For the IOI-HA, the IOI-HA norms from the VA ROES DALC database that contains over 100,000 IOI-HA records will be used. In the same fashion, we can select IOI-HA norms from ROES by based on degree of hearing loss and hearing aid style. A

logistic regression also will be conducted to examine if the proportion of responses differ between the groups on the specific telephone and exit survey items of interest.

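### Hypothesis 1b (outcomes at or above norm) rests on a Welch difference test with no margin or decision rule; at 25 per group, non-significance alone does not exclude a shortfall of about 0.4 SD

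*Combined protocol and SAP*

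**What the plan says.** The Purpose section, under Specific Aim 1, gives Hypothesis 1b as "Subjective outcomes from RECD coupler-based fittings will meet or exceed published norms".

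The Study 1 Data Analysis Plan provides one analysis against norms. For each group, the Session 3 outcomes are to be assessed by "comparing our mean, standard deviation, and sample size to those same variables from the published outcome respectively via a Welch test". Its purpose follows: "This will inform whether our outcomes for testbox fittings of replacement hearing aids from each group were consistent with the published norms or not". Norms for the IOI-HA come from a VA database that "contains over 100,000 IOI-HA records", from which norms can be selected by degree of loss and aid style. Norm sample sizes for the other instruments are not given.

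The Study 1 Power Analysis concerns a different endpoint: "The primary outcome of interest is based on fitting accuracy of each ear". Alpha 0.05 and power 0.80 are stated there and not for the comparison with norms.

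A second check on subjective outcomes compares replacement aids with the participant's current aids. The description of Session 1 (Study Interventions, Study 1) says that the baseline scores serve "to ensure the outcomes from the replacement hearing aids are at least equivalent". The planned analysis is a mixed-model repeated-measures ANOVA, also without a margin.

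**The concern.** Hypothesis 1b is a non-inferiority claim: it needs evidence that the group mean is not meaningfully below the norm. The null hypothesis of a Welch test is equality with the norm. The test can give evidence that a group differs from the norm, but failure to reject does not show that the norm is met. With a difference test as the only tool and a yes-or-no answer about consistency, non-significance is the obvious route to the favourable answer. A smaller or noisier sample then makes that answer more likely.

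Two-sided significance also does not by itself separate exceeding the norm from falling below it; the direction has to be read from the estimate.

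Hypothesis 1b is one of two named hypotheses under Aim 1. It bears on whether dropping the face-to-face fitting preserves patient-reported outcomes. A report that outcomes were consistent with norms could carry weight in adopting the service even where the data leave room for a material shortfall.

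**Working it through.** **Inputs from the plan.** The Study 1 Power Analysis needs 100 ears. That is 100/2 = 50 participants, or 50/2 = 25 per group with data. Enrolment adds 15%: 50 × 1.15 = 57.5, so 58, or 29 per group. There is no planned figure for the comparison with norms, so there is none to reproduce.

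**Assumptions, because the plan is silent.** Alpha 0.05, two-sided (one-sided 0.05 as a sensitivity check). Equal SDs in study group and norm sample. Norm sample size m between 100 and 100,000 for the main results. Shortfalls δ are in SD units.

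**Precision.**
- SE = √(1/n + 1/m).
- n = 25, m = 100,000: SE ≈ 0.200, Satterthwaite df ≈ 24, critical t = 2.064, so the half-width is 2.064 × 0.200 = 0.41 SD.
- n = 25, m = 100: SE = √(0.04 + 0.01) = 0.2236, df ≈ 36.9, critical t = 2.026, so the half-width is 0.45 SD.

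With very large norms, an observed mean exactly at norm therefore has an interval reaching 0.41 SD below it. Non-significance requires only that the observed difference lie within ±0.41 SD, so the lower limit could be as low as about 0.41 + 0.41 = 0.82 SD below norm.

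**Chance that a single test is non-significant.** The test statistic follows a noncentral t with noncentrality δ/SE. For example, δ = 0.3 with very large norms gives 0.3/0.2 = 1.5 and a detection probability of 0.30, so a miss rate of 0.70.

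| True shortfall | 25/group, m = 100,000 | 25/group, m = 100 | 29/group, m = 100,000 | 25/group, m = 100,000, one-sided 0.05 |
|---|---|---|---|---|
| 0.3 SD | 70% | 74% | 66% | 57% |
| 0.4 SD | 52% | 59% | 45% | 38% |
| 0.5 SD | 33% | 41% | 26% | 22% |
| 0.8 SD | 3% | 6% | 1% | 1% |

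With very large norms and the two-sided test, the miss rate crosses 50% at a shortfall of 0.41 SD. Simulation agreed: 73.5% at 0.3 SD with m = 100, 41.7% at 0.5 SD with m = 100, and 34.5% at 0.5 SD with m = 100,000.

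**What a margin rule would deliver at this size.** Success means that the unfavourable 95% limit clears a margin M. If truth equals the norm, the probability comes from the same noncentral t with noncentrality M/SE. For 25 per group and m from 100 to 100,000:

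| Assumed margin | Chance of success per scale |
|---|---|
| 0.3 SD | 26–30% |
| 0.4 SD | 41–48% |
| 0.5 SD | 59–67% |

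**The case against.** The strongest reply is that the plan never says Hypothesis 1b will be accepted when p exceeds 0.05. It says only that the test will inform whether outcomes were consistent with norms. That stands: acceptance on non-significance, and two-sidedness, are inferences. But no other rule is given, and the hypothesis cannot be judged without one.

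A reader might also infer that the test would usually pass outcomes that are clearly below norm. The figures do not support this. With large norms, a miss is more likely than not only for shortfalls up to about 0.4 SD. At 0.5 SD a shortfall is detected about two times in three, and at 0.8 SD almost always. The documents do not say what size of shortfall matters.

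Nor are these rates the error rate for Hypothesis 1b, which covers several instruments and two groups. Suppose every comparison had to be non-significant. With three scales correlated 0.3 to 0.7 (an assumption), a uniform 0.3 SD shortfall and a fixed norm, all three would be non-significant in about 41–53% of single groups, and about 17–28% of the time across both groups. The plan gives no combination rule, so neither the per-test nor the joint figure can be called its error rate.

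It is also fair that a large norm sample helps: at 0.5 SD the miss rate is 59% if the norm sample is 25 and 33% if it is 100,000. It cannot remove the uncertainty from the study group itself. Finally, fitting accuracy is the primary outcome and there is a within-person comparison with current aids. Both limit what depends on the norm test, but neither answers whether norms are met, and the current-aid comparison lacks a margin too.

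**Conclusion.** The point holds in a limited form. The stated method, a difference test without a margin, cannot support a hypothesis that outcomes are at or above norm, and the sample size was not set for that question. Under the assumptions above, an observed mean at norm would leave shortfalls of up to about 0.41 SD unexcluded (0.45 SD with a norm sample of 100). Neither a one-sided test nor full retention of 29 per group removes the problem.

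The documents do not support saying that the plan has committed to accepting Hypothesis 1b on non-significance, or that large shortfalls would usually go unnoticed. The change should be made before analysis. It does not affect the primary fitting-accuracy analysis.

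**What to change.** Amend the Study 1 Data Analysis Plan as follows.

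- For each scale and each group, report the difference from the norm with its 95% confidence interval.
- Fix and justify a margin for each scale before the outcome data are seen.
- Conclude that the norm is met or exceeded only if the confidence limit on the unfavourable side clears the margin. The unfavourable side depends on the scoring direction of each scale.
- Otherwise report the comparison as inconclusive, and do not read a non-significant Welch test as meeting the norm.
- Say whether Hypothesis 1b will be reported scale by scale and group by group, or what combination is required.
- State the chance of success at the chosen margins.

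The direct cost is plan wording and the work of justifying margins; no new data are needed. The real downside is that many comparisons may be inconclusive. At assumed margins of 0.3 or 0.4 SD that is the more likely result for each scale even if outcomes truly equal the norm. For scale, 80% power against a very large norm sample would need about 90, 52 or 34 per group at margins of 0.3, 0.4 or 0.5 SD. No added enrolment is proposed, since Study 1 is sized for fitting accuracy; an interval honestly reported as inconclusive is still more informative than a non-significant p-value.

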1a-Introduction. In the VA system, hearing loss is the second-most common service-connected condition affecting 933,182 Veterans, exceeded only by tinnitus which affects 1,121,709 Veterans (data from Veterans Benefit Report for Fiscal Year 2016). In FY 2016, the VA dispensed 750,075 hearing aids at a net procurement of nearly \$270 million (report generated from VA Denver Acquisition and Logistics Center [DALC] Remote Order Entry System [ROES]). Between November 2015 and October 2016, the VA dispensed 461,862 receiver-in-the-canal (RIC) behind-the-ear (BTE) hearing aids; 103,314 BTEs with open-fit coupling or custom earmolds; and 187,952 in-the-ear (ITE) style hearing aids (VA DALC, 2017). It is estimated that 50.1% of Veterans being fitted with new amplification are experienced VA hearing-aid users (Dennis, 2014). The Office of the Inspector General (OIG) recently audited the VA's hearing-aid services and found that the "VA was not timely in issuing new hearing aids to veterans" (OIG, 2014, p. i). One way to improve the timeliness in which Veterans receive their new amplification, without increasing the resources spent, is through an alternative hearing-aid fitting approach. We propose such an alternative fitting approach that aims to increase efficiency of hearing-aid

delivery to experienced users whilst maintaining the quality of the service provided via a standard-of-care approach.

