Participants may directly benefit from this protocol. They all will receive a comprehensive audiologic evaluation and those results will be placed in their medical record. For those in Study 1 and 3, their current hearing aids will be evaluated to ensure proper function and best fit. If in need of repair, maintenance, or adjustment, these will be made. Their replacement hearing aids will be carefully fitted and verified to best practices and they will receive close follow-up regarding them. They may enjoy the benefit of obtaining hearing aids without having to come into the clinic for a face-to-face visit (experimental groups only). If the results between the SoC and experimental groups are equivalent, then this study would provide an evidence-based, RECD fitting approach that will improve Veteran-Centric care. Specifically, the RECD-based delivery model reduces the number of visits required to fit a replacement hearing aid compared to the SoC delivery model and, therefore, should result in greater patient satisfaction and reduced costs. In addition, the reduction in the number of clinic visits for established hearing aid patients may produce a reduction in wait times (greater access to care) for new patients seeking audiology services. The risks to participants is less than minimal and the anticipated benefits outweigh the minimal risk.

Selection of Subjects

Study 1 and Study 3: Inclusion Criteria:

Participants will be included in the study if the following criteria are met:

1. aged 18-85 years
2. experienced hearing-aid users who are obtaining replacement VA-issued hearing aids of the same style as their current hearing aids
3. competent hearing aid skills as demonstrated via the checklist (See appendix)
4. no more than a moderate sensorineural hearing loss (defined as less than or equal to 60 dB HL pure-tone average at 500, 1000, and 2000 Hz AU)
5. symmetrical hearing between the ears as defined as no more than a 20 dB difference in pure-tone thresholds at two consecutive frequencies
6. >/=50% word-recognition abilities in quiet as measured during the diagnostic audiologic evaluation

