For Study 2, we are interested in making measures with these non-custom RIC and RITA hearing aids across a variety of ears of representative audiograms of open fit hearing aids. After further consideration, we decided to use the mean audiometric configurations from our previous multisite RR&D Merit Review examining open-fit hearing aids for the current Study 2. The participants do not have to have the actual loss for which we are fitting and verifying in this laboratory-based study, but have hearing loss similar to the audiogram they are assigned to reduce the risk of discomfort.

Vulnerable populations will NOT be recruited.

All studies will continue screen and consent until the targeted sample size of usable data is obtained (accounting for attrition) including 58 Veterans for Study 1; 106 Veterans for Study 2; and 88 Veterans for Study 3. See sample size estimates below.

Subject Recruitment

All subjects will be from the Durham VA audiology clinics. All potential participants will have an equal chance of being selected to participate in the study should they meet the inclusion/exclusion criteria (determined via preliminary chart review). Several recruitment methods will be utilized including through the audiology clinicians, letter, flyers, and signage.

The audiology clinicians will be informed of the study requirements for all three studies. If the clinician thinks the patient is a potential candidate for the study, then the clinician will ask if the patient wants to talk to a member of the study staff to learn more about the study. If the study staff member is available, then s/he will speak to the patient then. They potential participants can be consented at the VA at this time. If not, then the patient will be provided the recruitment letter and flyer and asked to contact the study staff. If the patient would like to be contacted by phone by the study staff, then the clinician will document their agreement to be contacted by phone in the clinical note.

Patients who are experienced hearing aid users scheduled in the audiology clinic to be considered for new amplification may be mailed the recruitment letter and flyer. In addition, Veterans who are eligible for new amplification (i.e., current hearing aids are > 4 years old)

based on a review of the hearing-aid ordering system (ROES) in CPRS, can be mailed a recruitment letter and flyer. These experienced hearing-aid users are required for Study 1 and 3.

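### The ROES norms for the IOI-HA in Study 1 are matched on hearing loss and aid style but not on hearing-aid experience, the trait that defines the sample

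*Combined protocol and SAP*

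**What the plan says.** Hypothesis 1b (Purpose, Specific Aim 1) reads: "Subjective outcomes from RECD coupler-based fittings will meet or exceed published norms". Under Selection of Subjects, Study 1 is limited to "experienced hearing-aid users who are obtaining replacement VA-issued hearing aids of the same style as their current hearing aids". Participants must also show "competent hearing aid skills as demonstrated via the checklist". At Session 1 the protocol adds: "If questions or concerns arise, then they will be re-oriented during this session or disqualified".

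The Study 1 Data Analysis Plan compares each group's Session 3 subjective outcomes with norms by a Welch test, using the mean, SD and sample size from each side. For the IOI-HA, the norms come from a VA ROES database of more than 100,000 records, and "we can select IOI-HA norms from ROES by based on degree of hearing loss and hearing aid style". These are the only two selection variables named.

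Section 1a (Introduction) gives the one figure on experience in the VA: an estimate that "50.1% of Veterans being fitted with new amplification are experienced VA hearing-aid users".

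**The concern.** The plan already accepts that the norms should resemble the sample, since it proposes to select them by degree of loss and by style. It leaves out experience, which is the first thing that separates Study 1 participants from VA hearing-aid recipients in general. If the IOI-HA records include first-time users, and if those users answer the IOI-HA differently from experienced users, the comparison with norms reflects who was enrolled as well as how the aids were fitted.

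Both Study 1 groups receive the testbox fitting, so there is no standard-of-care arm in which the same difference would cancel. The problem also does not depend on the form of the test: a non-inferiority margin applied to the same norm would carry the same bias. If experienced users score higher, a real shortfall of the testbox fitting could be hidden. If they score lower, the fitting could appear to fall below the norm when it does not.

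**Working it through.** **Figures in the documents**
- Experienced VA users among Veterans being fitted: 50.1% (section 1a). It is a cited estimate with no inputs, so it cannot be reproduced. Its complement is 100 − 50.1 = 49.9%.
- Study 1 size: 50 evaluable participants, so 50/2 = 25 per group, and 58 enrolled, so 58/2 = 29 per group (Study 1 Power Analysis).
- Norm file: over 100,000 records (Study 1 Data Analysis Plan).
- No power or sample size is stated for Hypothesis 1b, so there is no planned figure to reproduce.

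**Assumptions**
- Share *s* of first-time users in the IOI-HA records after the loss and style filters: 25% to 75%, with 49.9% as the middle case.
- Difference *d* (experienced minus new users) on the IOI-HA: 0.2 to 0.5 SD in absolute value, sign unknown.
- Two-sided alpha of 0.05. The plan states 0.05 for the fitting-accuracy calculation only and gives no sidedness for the Welch test.

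**Formulas**
- Shift in the norm mean, in SD units: *s* × *d*.
- Standard error with SD = 1: √(1/25 + 1/100,000) ≈ 0.200. The norm file adds almost nothing, so the degrees of freedom are about 24.
- Noncentrality: shift / SE. The rejection probability comes from the noncentral t distribution.

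**Rejection probability when the testbox group truly equals its experienced peers**

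| Share *s* | *d* (SD) | Shift (SD) | n = 25 | n = 29 |
|---|---|---|---|---|
| 25% | 0.2 | 0.05 | 5.7% | 5.8% |
| 25% | 0.5 | 0.125 | 9.2% | 10.0% |
| 49.9% | 0.1 | 0.05 | 5.7% | 5.8% |
| 49.9% | 0.2 | 0.10 | 7.7% | 8.1% |
| 49.9% | 0.3 | 0.15 | 11.1% | 12.2% |
| 49.9% | 0.5 | 0.25 | 22.4% | 25.4% |
| 75% | 0.2 | 0.15 | 11.1% | 12.2% |
| 75% | 0.5 | 0.375 | 43.6% | 49.6% |

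For example, 0.499 × 0.5 = 0.25 and 0.25 / 0.20 = 1.25, which gives 22.4%. With norms from experienced users only, the shift is 0 and the error is 5%.

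**Loss of sensitivity if experienced users score higher.** Suppose the testbox group is truly 0.5 SD below its experienced peers, with n = 25 and *s* = 49.9%. The shortfall is detected with probability 67% against matched norms, 48% if *d* = 0.2, and 22% if *d* = 0.5.

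**Precision after the extra filter.** With 50,000 records the norm contributes 1/50,000 = 0.00002 to the variance, against 1/25 = 0.04 from the study group. With only 1,000 records left in a stratum it would contribute 0.001, and the SE would be √0.041 ≈ 0.202 instead of 0.200.

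**The case against.** A reader might infer from the 50.1% that about half the norm pool is a different population. The documents do not support that. The figure describes all Veterans being fitted, not the IOI-HA records, and still less those records after filtering. The style filter alone changes the mix. In section 1a, receiver-in-the-canal aids are 461,862 of 461,862 + 103,314 + 187,952 = 753,128 aids, or 61%, and Study 1 covers in-the-ear and custom-earmold behind-the-ear aids. The remaining 49.9% may also include people who gained their experience outside the VA. The share is therefore an assumption.

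A reader might also infer that the plan commits to two filters and no others. The wording is permissive. It neither limits the selection to loss and style nor rules out experience, but it does not commit to experience either.

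The scope is limited. ROES supplies norms for the IOI-HA only, while Hypothesis 1b also covers other instruments. Fitting accuracy, the primary outcome, does not use these norms. The plan also compares replacement aids with each participant's current aids, which does not depend on any norm. That last comparison is a real safeguard, but it does not test Hypothesis 1b as worded.

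Finally, nothing in the documents shows that *d* differs from zero. At *d* = 0.1 and a 49.9% share the error is 5.7%, which is negligible.

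All of this stands and reduces the size and certainty of the point. It does not remove the mismatch: the sample is defined by experience, and the named selection variables omit it.

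**Conclusion.** The concern holds in a limited form. The selection named for the IOI-HA norms leaves out the trait that defines the Study 1 sample, so the IOI-HA part of Hypothesis 1b may mix a population difference with the effect of the testbox fitting.

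The size cannot be derived from the documents. Under the stated assumptions the norm shifts by 0.05 to 0.375 SD. At a share of about 50%, a nominal 5% error becomes about 8% to 22% with 25 per group. The direction is unknown, so it would be wrong to conclude that the plan favours the testbox fitting.

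It would also go too far to extend the point to the SADL and APHAB norms, because the documents do not describe the populations behind them.

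**What to change.** In the Study 1 Data Analysis Plan, prespecify that the IOI-HA norms are restricted to records from Veterans with a prior VA hearing-aid issue (replacement fittings), within the same degree-of-loss and style strata. Replace the permissive wording with a definite rule.

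There is some reason to expect this to be feasible. Under Subject Recruitment, Veterans whose current aids are more than 4 years old are identified "based on a review of the hearing-aid ordering system (ROES) in CPRS, can be mailed a recruitment letter and flyer". This does not show that prior issue is linked to the IOI-HA records, so the link should be checked before the rule is fixed. If it cannot be made, report that the mix of new and experienced users is unknown and label the IOI-HA norm comparison descriptive.

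The cost is one more filter on a data pull already planned, a few lines of text and a smaller norm file, with negligible loss of precision. The filter would not remove differences due to the skills check, word-recognition or cognitive criteria. Those should be stated as remaining limits of the comparison.
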